5.2 Publication

The sponsor will not unreasonably withhold consent to publish the data generated in this trial. However, it is the policy of the sponsor not to allow the investigators to publish their results or findings prior to the sponsor's publication of the overall trial results. The investigator agrees that before he/she publishes any results of this trial, he/she shall allow at least 45 days for the sponsor to review the prepublication manuscript prior to submission of the manuscript to the publisher, as

specified in the Clinical Trial Agreement between Institution/investigator and sponsor. In accordance with generally recognized principles of scientific collaboration, co-authorship with any company personnel will be discussed and mutually agreed upon before submission of a manuscript to a publisher.

6 **AUTHORITIES/ETHICS**

6.1 Regulatory Authorities

This trial will be submitted to the local regulatory authority for approval or notification whichever is applicable. The trial will only be undertaken in compliance with the local regulatory requirements.

6.2 Independent Ethics Committee/Institutional Review Board

This trial can only be undertaken after full approval of the protocol, informed consent/assent, any other written information given to subjects, and subject recruitment materials has been obtained from the IEC/IRB. This document must be dated and clearly identify the trial and the documents being approved.

During the trial the following documents will be sent to the IEC/IRB for their review:

- changes to the Investigator's Brochure;
- reports of adverse events that are serious, unlisted and associated with the investigational drug;
- DSUR and Quarterly Line Listings (EU member states only).

Substantial amendments and applicable Informed Consent/Assent Form revisions must promptly be submitted to the IEC/IRB for review and approval prior to implementation of the change(s), except when necessary to eliminate an immediate hazard to the trial subjects.

The IEC/IRB is responsible for continuous review of the trial. At least once a year, the investigator will provide the IEC/IRB with a progress report to allow review of the trial. Additional progress reports should be provided if required by the IEC/IRB.

These requests and (re)approvals, if applicable, should be documented in writing.

6.3 ICH-GCP Guidelines

This trial will be conducted in accordance with the current ICH-GCP Guidelines. GCP is an international ethical and scientific quality standard for designing, conducting, recording, and reporting trials that involve the participation of human subjects. Compliance with this standard provides public assurance that the rights, safety and well being of trial subjects are protected, consistent with the principles that have their origin in the Declaration of Helsinki, and that the clinical trial data are credible.

6.4 Subject Information and Informed Consent/Assent

Each subject or a legally acceptable representative must give written consent/assent according to local requirements after the nature of the study has been fully explained. The ICF(s) must be signed before performance of any study-related activity. The ICF(s) and assent form that is/are

used must be approved by both the sponsor and by the reviewing IEC/IRB and be in a language that the subject can read and understand. The informed consent/assent should be in accordance with principles that originated in the Declaration of Helsinki, current ICH and GCP guidelines, applicable regulatory requirements, and sponsor policy.

Before enrollment in the study, the investigator or an authorized member of the study-site personnel must explain to potential subjects or their legally acceptable representatives the aims, methods, reasonably anticipated benefits, and potential hazards of the study, and any discomfort participation in the study may entail. Subjects will be informed that their participation is voluntary and that they may withdraw consent/assent to participate at any time. They will be informed that choosing not to participate will not affect the care the subject will receive. Subjects will be told that alternative treatments are available if they refuse to take part and that such refusal will not prejudice future treatment. Finally, they will be told that the investigator will maintain a subject identification register for the purposes of long-term follow up if needed and that their records may be accessed by health authorities and authorized sponsor personnel without violating the confidentiality of the subject, to the extent permitted by the applicable law(s) or regulations. By signing the ICF the subject or legally acceptable representative is authorizing such access. It also denotes that the subject agrees to allow his or her study physician to recontact the subject for the purpose of obtaining consent/assent for additional safety evaluations and subsequent disease-related treatments, if needed. The physician may also recontact the subject for the purpose of obtaining consent to collect information about his or her survival status.

The subject or legally acceptable representative will be given sufficient time to read the ICF and the opportunity to ask questions. After this explanation and before entry into the study, consent/assent should be appropriately recorded by means of either the subject's or his or her legally acceptable representative's personally dated signature. After having obtained the consent/assent, a copy of the ICF must be given to the subject.

If the subject or legally acceptable representative is unable to read or write, an impartial witness should be present for the entire informed consent process (which includes reading and explaining all written information) and should personally date and sign the ICF after the oral consent/assent of the subject or legally acceptable representative] is obtained.

Children (minors) or subjects who are unable to comprehend the information provided can be enrolled only after obtaining consent/assent of a legally acceptable representative. Assent must be obtained from children (minors) capable of understanding the nature of the study, typically subjects 7 years of age and older, depending on the institutional policies. Written assent should be obtained from subjects who are able to write. A separate assent form written in language the subject can understand should be developed for adolescents. After having obtained the assent, a copy of the assent form must be given to the subject, and to the subject's parent or if applicable legally acceptable representative.

When prior consent/assent of the subject is not possible and the subject's legally acceptable representative is not available, enrollment procedures should be described in the protocol with documented approval/favorable opinion by the IEC/IRB to protect the rights, safety, and well-being of the subject and to ensure compliance with applicable regulatory requirements. The subject or legally acceptable representative must be informed about the study as soon as possible and give consent/assent to continue.

6.5 Privacy of Personal Data

The processing of personal data in pursuit of this trial will be limited to those data that are reasonably necessary to investigate the efficacy, safety, quality, and utility of the investigational product(s) used in this trial. These data will be processed with adequate precautions to ensure confidentiality.

The sponsor ensures that the personal data are:

- collected for a specified and legitimate purpose;
- processed fairly and lawfully;
- credible.

Explicit consent for the processing of personal data will be obtained from the participating subjects or their legally acceptable representative prior to any processing of personal data.

The sponsor or its representatives whose responsibilities require access to personal data are obliged to keep the identity of trial subjects confidential. This confidentiality will be maintained throughout the complete data processing. Trial subjects will be entitled to request confirmation of the existence of personal data held by the sponsor and will have the right to rectify erroneous or inaccurate data.

7 FINANCING AND INSURANCE

7.1 Financial Disclosure

The disclosed financial interest of the investigator must be collected before enrollment of the first subject. The investigator should promptly update this information if any relevant changes occur up to 1 year following trial completion.

Disclosable financial interests will be recorded on the Investigator Financial Disclosure Form.

Any investigator(s) added as investigational staff must complete the Investigator Financial Disclosure Form at the beginning of their participation in the trial. For any investigator(s) leaving the site prior to trial completion, an Investigator Financial Disclosure Form should be obtained at the end of their participation.

7.2 Indemnification

The sponsor undertakes to indemnify and hold harmless the investigator and his/her medical staff from any claim, demand or cost arising from the activities to be carried out in compliance with the protocol, as further specified in the Clinical Trial Agreement.

7.3 Insurance

The sponsor ensures that appropriate liability insurance is available covering injuries arising from the participation of the trial subject in this trial, as further specified in the Informed Consent/Assent and the Clinical Trial Agreement.

Not applicable; this is the initial version of this Statistical Analysis Plan

ABBREVIATIONS

3TC lamivudine ABC abacavir

ADR adverse drug reaction
AHA American Heart Association

ALP alkaline phosphatase ALT alanine aminotransferase

ARV antiretroviral

ASR Annual Safety Report
AST aspartate aminotransferase

AUC area under the plasma concentration-time curve

AUC_{12h} area under the plasma concentration-time curve from time of intake until

12 hours after dosing

AZT zidovudine

b.i.d. twice daily (bis in die)

BRAT bananas, rice, applesauce and toast

CDC US Centers for Disease Control and Prevention

C_{0h} predose plasma concentration
C_{max} maximum plasma concentration
C_{min} minimum plasma concentration

CRF Case Report Form
DAIDS Division of AIDS
DCF Data Correction Form
drug-induced liver injury

DRV darunavir (formerly known as TMC114)
DSUR Development Safety Update Report

FTC emtricitabine

GCP Good Clinical Practice HDL high-density lipoprotein

HIV human immunodeficiency virus

ICH International Conference on Harmonisation

IEC Independent Ethics Committee
INR international normalized ratio
IRB Institutional Review Board

IUD intra-uterine device

LC-MS/MS liquid chromatographic mass spectrometry/mass spectrometry

LDL low-density lipoprotein

LPV lopinavir

NCEP National Cholesterol Education Program

NCR non-carbon required

NNRTI non-nucleoside reverse transcriptase inhibitor NRTI nucleoside/nucleotide reverse transcriptase inhibitor

OBR optimized background regimen

PI protease inhibitor

QA	Quality Assurance
QC	Quality Control
q.d.	once daily (quaque die)
RAM	resistance-associated mutation
RBC	red blood cell
rtv	low-dose ritonavir
SJS	Stevens-Johnson syndrome
TEN	toxic epidermal necrolysis

toxic epidermal necrolysis upper limit of laboratory normal range white blood cell ULN

WBC

1. INTRODUCTION

This statistical analysis plan (SAP) contains definitions of analysis sets, derived variables, and statistical methods for the CSR analysis (final analysis) of the continued access trial TMC114IFD3001.

1.1. Trial Objectives

Primary Objective

The primary objective of this trial was to continue the provision of DRV/rtv for adult and pediatric subjects who previously received DRV/rtv in the clinical (parent) trials TMC114-C211, TMC114-C214, TMC114-TiDP31-C229 or in the pediatric (parent) trial TMC114-TiDP29-C232, who continued to benefit from the use of DRV/rtv, in countries where DRV is not commercially available for the subject, is not reimbursed, or cannot be accessed through another source (e.g., access program, governmental program).

In addition, the long-term safety and tolerability of DRV/rtv in combination with other ARVs was to be assessed.

1.2. Trial Design

This was a continued access trial for adult and pediatric subjects who have completed treatment with DRV/rtv in the adult clinical (parent) trials TMC114-C211, TMC114-C214, TMC114-TiDP31-C229 or in the pediatric (parent) trial TMC114-TiDP29-C232, who continued to benefit from the use of DRV/rtv, and who lived in a country where DRV is not accessible.

At the baseline visit, inclusion and exclusion criteria were to be checked to confirm eligibility. Once the eligibility criteria were met, subjects were to continue treatment as follows:

- HIV-1 infected subjects participating in the TMC114-C211(parent) trial or in the pediatric (parent) trial TMC114-TiDP29-C232, after original participation in TMC114-TiDP29-C230 trial were to continue on the DRV/rtv 800/100 mg q.d. dosing regimen as administered in the original (parent) trial.
- HIV-1 infected subjects participating in the pediatric (parent) trial TMC114-TiDP29-C232, after original participation in TMC114-C212 or TMC114-TiDP29-C228 trial were to continue on the selected b.i.d. DRV/rtv dosing regimen as administered in the original (parent) trial, or on an adjusted dose if necessary due to a change in body weight.
- HIV-1 infected subjects participating in the TMC114-C214 or TMC114-TiDP31-C229 (parent) trials were to continue on the DRV/rtv 600/100 mg b.i.d. dosing regimen as administered in the original (parent) trial.

Treatment was to be continued until one of the following criteria was met (whichever occurs first):

- Virologic failure;
- Treatment-limiting toxicity;

- Loss to follow-up;
- Withdrawal of consent/assent by the subject or withdrawal of consent by the parent(s)/ legal representative(s);
- Pregnancy;
- Termination of the trial by the sponsor;
- A DRV-based treatment regimen became commercially available for the subject and was reimbursed, or could be accessed through another source (e.g., access program, government program) in the region the subject was living in or subjects could be switched to local standard of care, as appropriate.

A post-treatment follow-up contact was to be performed 4 weeks after the last dose of trial medication for subjects with an ongoing adverse event, that discontinue the trial under Protocol Amendment 1.

Adverse event reporting was restricted to the following (or all AEs if applicable per local regulation):

- Adverse events considered at least possibly related to DRV/rtv;
- Adverse events leading to discontinuation or treatment interruption;
- Serious adverse events and pregnancies.

Efficacy and safety laboratory assessments were done locally, and were not transferred into the database for formal analysis purposes.

1.3. Statistical Hypotheses for Trial Objectives

Not applicable.

1.4. Sample Size Justification

Not applicable.

Subjects who previously received treatment with DRV/rtv in the clinical (parent) trials TMC114-C211, TMC114-C214, TMC114-TiDP31-C229 or in the pediatric (parent) trial TMC114-TiDP29-C232, who continued to benefit from the use of DRV/rtv, and who lived in a country where DRV was not accessible might have been eligible to continue treatment with DRV/rtv via this trial.

1.5. Randomization and Blinding

Randomization

Since this was a continued access single arm trial, randomization procedures were not applicable.

Blinding

Since this was an open label, continued access trial, blinding procedures were not applicable.

7

2. GENERAL ANALYSIS DEFINITIONS

2.1. Visit Windows

2.1.1. Trial Phases

Analysis phases are constructed as per Table 1.

Table 1: Analysis Phases:

Trial phase	Start date	End date
Treatment	Date of first DRV intake in trial	If the subject died: min (date of last DRV + 2 days; date of death) If the subject permanently stopped the trial medication: minimum of: • date of last DRV intake + 2 days, if missing, date of discontinuation + 2 days • date of last contact
Follow-up (not defined when derived End date is before Start date of this phase)	End date of DRV Treatment phase + 1 day	If the subject died : date of death Otherwise: date of last contact

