5.5.3 AST AND ALT ELEVATIONS

A summary of AST and ALT elevations is provided in Table 7 below.

Note: For grade 3 or 4 laboratory toxicities, subjects should have a confirmatory measurement within 48 hours after the laboratory results become available. This management scheme is for confirmed laboratory abnormalities and not for isolated events.

Grade 3 AST or ALT elevations ($> 5.0 - \le 10.0 \times ULN$):

Subjects are to interrupt all medication (including DRV/rtv and background regimen) except if they are coinfected with hepatitis B or C (see below). Upon resolution of the laboratory abnormality to within 1 grade level (\leq grade 2), the subject may resume all trial medication under the guidance of the investigator and after discussion with a sponsor physician.

If after a grade 3 elevation, the subject has a recurrence of a grade 3 or 4 increase in AST or ALT after restarting trial medications, he/she will permanently discontinue the medication (including DRV/rtv and background regimen) and will be withdrawn from the trial.

Subjects with concomitant hepatitis B and with emtricitabine (FTC) or lamivudine (3TC) as a component of the background regimen:

Warning: Severe acute exacerbations of hepatitis B have been reported in subjects who are co-infected with hepatitis B virus and HIV and have discontinued FTC or 3TC. Hepatic function should be monitored closely with both clinical and laboratory follow-up for at least several months in subjects who discontinue FTC or 3TC and are co-infected with hepatitis B virus and HIV. If appropriate, initiation of anti-hepatitis B therapy may be warranted.

Subjects with concomitant hepatitis A, B, C, or E:

Subjects with concomitant acute hepatitis A infection diagnosed at or after baseline have to be excluded. If acute viral hepatitis is diagnosed while on trial, the subject must be withdrawn immediately and the necessary follow-up visits performed.

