5.5.4.2 Viral Hepatitis

If acute viral hepatitis is diagnosed while on trial, the subject should be permanently withdrawn from the trial.

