5.6.5 PANCREATITIS

Pancreatitis must be considered whenever a subject develops abdominal pain, nausea, vomiting, and/or elevated amylase or lipase. Temporary treatment interruption is allowed (including DRV/rtv and background regimen) in case of clinical suspicion and until the diagnosis of pancreatitis can be excluded.

It is not recommended to co-administer tenofovir disoproxil fumarate (TDF) and didanosine (ddI) in the OBR (if applicable) due to an increased risk of pancreatitis¹⁴.

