4. SAFETY

Safety results will be summarized for the Treatment phase; all safety data (including Follow-up phase) will be included in listings.

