4.1. Adverse Events

4.1.1. Analysis Methods

AE incidence (count and percentage) will be tabulated, overall and by preferred term/SOC.

Overall AE Summary tables and tables by preferred term/SOC for serious events, AEs leading to discontinuation, AEs at least grade 3, HIV-related AEs, and AEs at least possibly related to DRV will be presented throughout the treatment phase only; any AEs in the Follow-up phase will be listed only.

The dictionary used for adverse events will be MedDRA version 23.0.

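### The table of AEs leading to discontinuation can miss an AE that starts during a DRV interruption and prevents restart, because the SAP closes the Treatment phase 2 days after the last intake

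*SAP*

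**What the plan says.** SAP 2.1.1, Table 1 defines a single Treatment phase that starts at the first DRV intake in the trial. For a subject who permanently stopped, it ends at the earlier of last contact and "date of last DRV intake + 2 days, if missing, date of discontinuation + 2 days". For a subject who died, the last intake plus 2 days is capped at the date of death. Follow-up begins at "End date of DRV Treatment phase + 1 day". A gap in dosing has no rule of its own.

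SAP 4 sets the general principle: "Safety results will be summarized for the Treatment phase; all safety data (including Follow-up phase) will be included in listings". SAP 4.1.1 applies it to the AE tables, naming AEs leading to discontinuation among them. These tables "will be presented throughout the treatment phase only; any AEs in the Follow-up phase will be listed only".

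Protocol 5.7.2.3 commits to a safety summary that includes AEs leading to discontinuation. It sets no window around the last dose.

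Several toxicity sections of the protocol (5.5.3, 5.5.6, 5.5.7, 5.5.8, 5.6.5) interrupt treatment and leave the question of restart for later. For grade 3 AST or ALT, for example, 5.5.3 says: "Subjects are to interrupt all medication (including DRV/rtv and background regimen) except if they are coinfected with hepatitis B or C". Protocol Part II, 1.4 requires a change in the severity of an existing AE to be entered as a new AE.

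**The concern.** The date of last intake is known only in hindsight. During an interruption nobody can say whether the Treatment phase is still open. It stays open if a later dose is taken. If none is taken, it closed 2 days after the dose before the interruption. Two subjects with the same interruption and the same AE on the same off-drug day can therefore be classified differently because of what happened afterwards.

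This matters most for the discontinuation table. An AE that arises off drug and rules out a restart is an event that table exists to count, and it is also the event that leaves the phase closed. AE collection in this trial is restricted to a few categories, one of which is AEs leading to discontinuation or interruption. Laboratory safety results were not transferred for formal analysis (SAP 1.2). The AE tables thus carry most of the evidence on the long-term safety and tolerability aim, and Protocol 5.7.2 plans no further statistical analysis once data collection ends.

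**Working it through.** The plan has no figure to reproduce: sample size and hypotheses are stated as not applicable. The check applies the Table 1 rule to one interruption with two outcomes.

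**Inputs**
- Treatment end = min(last DRV intake + 2 days, last contact), or min(last DRV intake + 2 days, death) if the subject died (SAP Table 1).
- Follow-up start = Treatment end + 1 day (SAP Table 1).
- AE allocation by onset date. This is an assumption, because the SAP gives a phase rule for concomitant medications only (SAP 3.5).
- Illustrative days: last dose before the interruption on day 100. Either DRV is restarted on day 121, last taken on day 700, with last contact on day 730; or it is never restarted, with last contact on day 130.

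**Phase end**
- Restarted: min(700 + 2, 730) = day 702.
- Never restarted: min(100 + 2, 130) = day 102, so Follow-up starts on day 103.
- Never restarted, death on day 130: min(100 + 2, 130) = day 102.

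**Where an AE falls**

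| AE onset | Off-drug day | DRV restarted | DRV never restarted (alive or died) |
|---|---|---|---|
| Day 102 | 2 | Treatment, tabulated | Treatment, tabulated |
| Day 103 | 3 | Treatment, tabulated | Follow-up, listed only |
| Day 110 | 10 | Treatment, tabulated | Follow-up, listed only |
| Day 128 | 28 | not applicable (back on DRV) | Follow-up, listed only |

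The split begins on off-drug day 3. It would be the same if AEs were allocated by overlap of start and end dates, as SAP 3.5 does for medications: an AE that starts on day 110 cannot overlap a phase that closed on day 102.

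**Which events are exposed.** The toxicity that triggered the interruption began on drug, so it is tabulated either way. What can be missed is a separate AE first arising on off-drug day 3 or later, or a worsening of the trigger that Part II, 1.4 turns into a new AE. A document-based case: a related grade 3 event leads to interruption on day 100 and becomes grade 4 on day 107. It is then a new AE. Section 5.5.8 provides for permanent discontinuation at grade 4, subject to its listed exceptions. Since 107 > 102, the AE is in Follow-up. If the grade 3 record carries only the interruption, the subject has no entry in the discontinuation table.

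**The case against.** The case against a larger claim is strong, and most of it stands.

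A reader might infer that the rule generally removes the events that ended treatment. The protocol's own routes do not support this. In 5.6.5.2, treatment ends because the enzyme elevation persists or recurs. In 5.5.3, withdrawal after a grade 3 elevation follows recurrence after restart, hence on drug. In 5.5.6 to 5.5.8, non-resolution of a grade 3 event is the same AE. On these routes the decisive event normally has an on-drug onset and stays in the tables.

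Some tempting examples are weak. Section 5.5.4.2 says: "If acute viral hepatitis is diagnosed while on trial, the subject should be permanently withdrawn from the trial". If the diagnosis follows an interruption for raised ALT, though, its onset may well be dated to the ALT rise. Likewise 5.6.5 allows interruption "in case of clinical suspicion and until the diagnosis of pancreatitis can be excluded", and the symptoms or enzyme rises behind that suspicion are already present.

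A reader might also turn the off-drug days beyond day 2 into a percentage of AEs lost. That would be a share of calendar days. The documents give no rate of interruptions or of events within them.

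Nor are the events lost: they are listed, and SAP 3.2 reports reasons for discontinuation from the trial. Those reasons do not supply the preferred term, SOC or grade, so they only partly replace the AE table.

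Finally, this is a single-arm continued-access trial with no hypothesis, and a window of last dose plus a lag is clear and reproducible. That limits the consequence. It does not explain why a table defined by the event's effect on treatment should also be limited by onset date.

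**Conclusion.** The point holds in a narrow form. The table of AEs leading to discontinuation can omit a new or newly recorded AE that starts more than 2 days after the last dose and prevents restart. The same AE would be tabulated had DRV been resumed. Protocol 5.7.2.3 does not provide for that restriction.

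This rests on two assumptions: AEs are allocated by onset date, which the SAP does not state, and the discontinuation is attributed to the later AE record and not to the event that triggered the interruption. The number of subjects affected is unknown, may be small and could be zero.

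The documents do not support a conclusion that the AE tables as a whole are materially biased, or that Table 1 must be redefined. The other AE tables share the same window, but a fixed lag after last dose is an ordinary definition of on-treatment for them.

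**What to change.** Add two statements to SAP 4.1.1:
- AEs are allocated to analysis phases by date of onset.
- AEs leading to permanent discontinuation of DRV/rtv are tabulated regardless of onset date or phase.

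Leave Table 1 and the exposure definition in SAP 3.4 unchanged. Moving the phase end to a date of permanent discontinuation is not advisable. The SAP does not define that date, and visits may be up to 6 months apart, so the added time could depend on visit timing. The phase end also feeds the exposure formula and the ARV table.

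The cost is two sentences and a change of selection for one table. No further data collection is needed, and no treatment rule changes. The downside is that this table may include a few AEs with onset more than 2 days after the last dose; a footnote can identify them.
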